## PRÉCIS

### Background:

- The myelodysplastic syndromes (MDS) are a group of clonal bone marrow neoplasms characterized by ineffective hematopoiesis, cytopenia, and high risk of transformation to acute myeloid leukemia (AML).
- The median survival of patients with newly-diagnosed higher-risk MDS (HR-MDS) according to the Revised International Prognostic Scoring System (IPSS-R) is 1.5 years.
- Hypomethylating agents (HMAs), such as azacitidine and decitabine, are the standard of care therapy for HR-MDS. However, less than half of patients respond to HMAs, and even the best responses are transient and non-curative.
- The only curative treatment for patients with MDS is allogeneic hematopoietic stem cell transplantation (HSCT); however only a small portion are eligible for transplant.
- More effective therapies are needed for patients with HR-MDS.
- A promising approach for improving HMA efficacy in the treatment of MDS is by exploiting therapeutic synergism in combinatorial approaches.
- Inqovi (decitabine-cedazuridine) is an oral formulation of decitabine plus cytidine deaminase inhibitor that was recently FDA-approved for MDS, based on a similar safety and efficacy profile to decitabine for injection.
- KPT-8602 (eltanexor) is an orally-available, second-generation selective inhibitor of nuclear export (SINE) that covalently binds to exportin 1 (XPO1).
- XPO1 is a protein that mediates the nuclear export of molecules from the nucleus to the cytoplasm of the cell. Among affected molecules are tumor suppressor genes, mRNAs encoding oncogenes (including c-MYC), and newly assembled ribosomal subunits.
- By interfering with c-MYC translation, KPT-8602 may diminish rebound methylation after decitabine cessation and improve treatment responses in patients with MDS.
- Preliminary reports from a Phase 1/2 trial of KPT-8602 monotherapy in patients with higher-risk MDS who have failed HMAs show anti-tumor activity and an acceptable toxicity profile.
- Sequential addition of KPT-8602 to Inqovi may improve treatment responses in patients with MDS by acting synergistically to inhibit further DNA methylation.

### Objective:

- Phase I: To determine the recommended phase 2 dose (RP2D) of KPT-8602 in combination with Inqovi in adult participants with with higher-risk MDS
- Phase II: To determine overall response rate (ORR) of KPT-8602 in combination with Inqovi in adult participants with with higher- risk MDS

### Eligibility:

- Participants must have histologically or cytologically confirmed MDS according to 2016 WHO criteria ([1](#)), and for both Phase I and II:
  - have HR-MDS (IPSS-R > 3.5) with inadequate response to hypomethylating agent (HMA) therapy [(received  $\geq$  4 cycles of the standard dose (35 mg decitabine and 100 mg cedazuridine) without prior dose-reductions, with failure to achieve at least a PR or experienced disease progression prior to completing 4 cycles)]
- Age  $\geq$  18 years

- ECOG performance status  $\leq 2$  (KPS  $\geq 60$ )

**Design:**

- Participants with HR-MDS will be enrolled in both Phase I and II.
- Participants will be treated with Inqovi at a fixed dose of 1 tablet (35 mg decitabine and 100 mg cedazuridine) daily on Days 1-5 of each 28-day cycle, followed by KPT-8602 at escalating doses (Phase I) or the RP2D (Phase II).
- In Phase I, KPT-8602 will be dose-escalated following a standard 3+3 design, with a starting dose level of 10 mg for 10 days (staggered) within a cycle. If tolerated, the dose will be escalated to 14 days per cycle, or dose de-escalated to 5 mg at 14 or 10 days.
- This study will be done at the NIH Clinical Center with an enrollment of up to 80 planned participants.

## **STATEMENT OF COMPLIANCE**

The trial will be carried out in accordance with International Council on Harmonisation Good Clinical Practice (ICH GCP) and the following:

- United States (US) Code of Federal Regulations (CFR) applicable to clinical studies (45 CFR Part 46, 21 CFR Part 50, 21 CFR Part 56, 21 CFR Part 312, and/or 21 CFR Part 812)

National Institutes of Health (NIH)-funded investigators and clinical trial site staff who are responsible for the conduct, management, or oversight of NIH-funded clinical trials have completed Human Subjects Protection and ICH GCP Training.

The protocol, informed consent form(s), recruitment materials, and all participant materials will be submitted to the Institutional Review Board (IRB) for review and approval. Approval of both the protocol and the consent form must be obtained before any participant is enrolled. Any amendment to the protocol will require review and approval by the IRB before the changes are implemented to the study. In addition, all changes to the consent form will be IRB-approved; an IRB determination will be made regarding whether a new consent needs to be obtained from participants who provided consent, using a previously approved consent form.

## **1 INTRODUCTION**

### **1.1 STUDY OBJECTIVES**

#### **1.1.1 Primary Objective**

- Phase I: To determine the recommended phase 2 dose (RP2D) of KPT-8602 in combination with Inqovi in adult participants with higher-risk MDS
- Phase II: To determine the overall response rate (ORR) of KPT-8602 in combination with Inqovi in adult participants with higher-risk MDS

#### **1.1.2 Secondary Objectives**

- Phase I: To characterize the pharmacokinetic (PK) properties of KPT-8602 in combination with Inqovi (decitabine-cedazuridine) in MDS participants
- Phase II: To further evaluate the PK properties and safety of KPT-8602 in combination with Inqovi (decitabine-cedazuridine) in MDS participants

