### 3.1.2 Dose Escalation

In a phase I/II study (NCT 02649790) that evaluated single agent eltanexor in higher-risk MDS, 2 doses were evaluated: 5 patients received 10 mg and 15 patients received 20 mg, every day for 5 days per week of a 28-day cycle. The majority of patients were aged  $\geq 75$  and all were treated and refractory to hypomethylating agents. None of the patients experienced dose-limiting toxicities (DLTs) and the RP2D for eltanexor was selected as 10 mg given on days 1-5 of each week of a 28-day cycle in HR-MDS (20/28 days). Given the overlap in toxicities, particularly hematologic, between hypomethylating agents and eltanexor, our starting dose was set at 10 mg PO daily on Days 8-12 and Days 15-19 (total of 10 days per 28-day cycle as opposed to 20 days per 28-day cycle in NCT 02649790).

In Phase I, dose escalation will proceed in cohorts of 3-6 participants. The MTD is the dose level at which no more than 1 of up to 6 participants experience DLT during the first cycle (28 days) of treatment, and the dose below that at which at least 2 (of  $\leq 6$ ) participants have DLT as a result of the drug.

Participants in Cohort 1 will be eligible for the DLT evaluation if  $\geq 90\%$  (9 out of 10 doses) of KPT-8602 and  $\geq 80\%$  (4 out of 5 doses) of Inqovi were taken within the DLT period. Participants not evaluable for toxicity, will be replaced in the dose level.

Dose Escalation Schedule	
Dose Level	Dose of KPT-8602
Level -2	5 mg PO daily on Days 8-12 and Days 15-19
Level -1	5 mg PO daily on Days 8-21
Level 1 (starting dose)	10 mg PO daily on Days 8-12 and Days 15-19
Level 2	10 mg PO daily on Days 8-21

Dose escalation will start at dose level 1 and follow the rules outlined in the Table below.

Number of Participants with DLT at a Given Dose Level	Escalation Decision Rule
0 out of 3	Enter up to 3 participants at the next dose level
$\geq 2$	Dose escalation will be stopped. This dose level will be declared the maximally administered dose (highest dose administered). Up to three (3) additional participants will be entered at the next lowest dose level if only 3 participants were treated previously at that dose.

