## 5 CORRELATIVE STUDIES FOR RESEARCH

Participants may submit none, all, or a portion of research specific biospecimens to stay on study. Providing *all* research biospecimens is not a criterion for study inclusion and all samples are optional with the exception of pharmacokinetic (PK) samples. Any unused biological sample or derivative that is obtained from a participant during a clinical procedure on this study may be used for research and/or stored for future research purposes.

Every effort will be made to collect all research samples, including bone marrow aspirates and peripheral blood draws, at the time of a scheduled diagnostic bone marrow aspirate or blood draw for clinical purposes as listed in the study calendar and table below.

If additional tests are done for clinical purposes, additional samples will be collected also at that time(s), if feasible, and used for research.

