#### 5.2.1.2 Phase II

In Phase II, PK sampling schedules at the RP2D of KPT-8602 will be the same as planned in Phase I.

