## 10 STATISTICAL CONSIDERATIONS

### 10.1 OBJECTIVES AND ENDPOINTS

OBJECTIVES	ENDPOINTS	JUSTIFICATION FOR ENDPOINTS
Primary		
Phase I: To determine the recommended phase 2 dose (RP2D) of KPT-8602 in combination with Inqovi in adult participants with higher-MDS	- Recommended phase 2 dose (RP2D), as determined by the number of participants with DLTs reported at each dose level studied (Section 3.1.1 ) -Any toxicities identified from Day 1 of study drug through 28 days after the first dose. AEs are reported by type and grade. -ORR (defined as CR+PR+mCR with HI) per each cohort Responses will be assessed after every cycle with CBC and at the end of Cycles 2 and 6 with bone marrow assessment during treatment and every 3-6 months after that until time of disease relapse, disease progression, or death, or 8 years, whichever occurs first.	Standard endpoint for Phase I protocol Efficacy evaluation, standard for Phase II protocol
Secondary		
Phase I: To characterize the PK properties of KPT-8602 in combination with Inqovi in MDS participants	-AUC, half-life, and steady state concentration, measured by the KPT-8602 blood concentration 1, 2, 3, 4, 8, 24 and 48 hours after the product administration on days 8 and 21 of cycle one	PK studies to evaluate for adequate absorption of therapy and further define half-life/AUC and other properties of the study drug, when given in combination with Inqovi
Phase II: To further evaluate the PK properties and safety of KPT-8602 in combination with Inqovi in MDS participants	-Safety, as measured by: Incidence of AEs, SAEs; and AEs leading to discontinuation, death, and laboratory abnormalities, assessed at least weekly through cycle 3 and then at the start and every cycle after that	Confirm safety of the study drug at the RP2D
Exploratory		
To evaluate the relationship between KPT-8602 exposure (PK) and response	Each of these will be evaluated using descriptive methods and reported as exploratory results. If any statistical	Evaluate mechanism of the study drug, target engagement,

OBJECTIVES	ENDPOINTS	JUSTIFICATION FOR ENDPOINTS

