### 10.4.3 Analysis of the Secondary Endpoints

- The secondary objectives for phase I are to describe pharmacokinetic properties of KPT-8602 in MDS participants and to evaluate safety and tolerability of KPT-8602 in combination with Inqovi in MDS participants. The AUC, half-life, and Css of KPT-8602 will be evaluated in participants, by dose level using descriptive statistics.
- The secondary objectives for phase II are to evaluate the safety and tolerability of the agent as measured by the grades and types of toxicity noted for the agent at each dose level and reported descriptively.

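### Phase II has a PK objective with mandatory sampling but no PK endpoint or secondary analysis, and the Phase I summary by dose level splits identical first-dose conditions

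*Combined protocol and SAP*

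**What the plan says.** **Objective.** Section 1.1.2 gives Phase II two secondary aims, PK and safety: "Phase II: To further evaluate the PK properties and safety of KPT-8602 in combination with Inqovi (decitabine-cedazuridine) in MDS participants". The objectives column of the table in 10.1 repeats both.

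**Sampling.** Section 5.2.1.2 states: "In Phase II, PK sampling schedules at the RP2D of KPT-8602 will be the same as planned in Phase I". Section 5 makes these the only compulsory research samples: "all samples are optional with the exception of pharmacokinetic (PK) samples".

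**Endpoints.** In 10.1 the PK endpoint (AUC, half-life, steady-state concentration) stands in the Phase I row only and refers to cycle 1: "measured by the KPT-8602 blood concentration 1, 2, 3, 4, 8, 24 and 48 hours after the product administration on days 8 and 21". The Phase II row lists adverse events, discontinuations, deaths and laboratory abnormalities. Its justification is "Confirm safety of the study drug at the RP2D".

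**Analysis.** The Phase I bullet of 10.4.3 reads: "The AUC, half-life, and Css of KPT-8602 will be evaluated in participants, by dose level using descriptive statistics". The Phase II bullet begins: "The secondary objectives for phase II are to evaluate the safety and tolerability of the agent". It does not mention PK.

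**Dose levels.** Section 3.1.2 defines level 1 as "10 mg PO daily on Days 8-12 and Days 15-19". Level 2 is 10 mg daily on Days 8-21. Levels -1 and -2 are the matching 5 mg schedules.

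**The concern.** There are two linked gaps.

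First, a stated secondary objective has no endpoint and no secondary analysis, while the blood for it is drawn from every Phase II participant. An analyst who follows 10.1 and 10.4.3 would produce no Phase II PK result. One who notices the gap would have to choose the parameters and the summary after seeing the data. The Phase II bullet of 10.4.3 also speaks of toxicity at each dose level, although Phase II uses one dose. This suggests that the section was not brought into line with 1.1.2.

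Second, the level-by-level summary separates participants who are in the same PK condition at their first dose. The levels differ in schedule as well as in milligrams, and at the C1D8 profile only the milligrams matter. Splitting by level makes a small group smaller without distinguishing anything.

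Section 1.2.3.3 says that PK, with PD, safety and MTD interpretation, will inform optimal dosing in later trials, so the precision of these summaries has a use beyond this study.

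**Working it through.** **1. Tracing the Phase II PK objective**

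| Place | Phase II PK present? |
|---|---|
| 1.1.2, objective | Yes |
| 10.1, objective column | Yes |
| 5 and 5.2.1.2, sampling | Yes, compulsory, same as Phase I |
| 10.1, endpoint column | No, safety only |
| 10.4.3, Phase II bullet | No, safety and tolerability only |
| 1.1.3 and 10.4.9, exploratory | Exposure-response objective with no phase limit; generic descriptive method |

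From the table in 5.1, cycle 1 has 7 distinct samples around C1D8, plus 6 around C1D12 (levels 1 and -2) or 7 around C1D21 (levels 2 and -1). Two later troughs follow. That is 15 or 16 draws per participant.

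**2. Is C1D8 the same condition within a mg dose?**

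Levels 1 and 2 both give the first 10 mg on Day 8, and levels -1 and -2 both give the first 5 mg on Day 8. In 5.1 the C1D8 post-dose times are 1, 2, 3, 4, 8 and 24 h for all four levels. The schedules first diverge on Day 13, so the C1D8 profile does not depend on schedule. The second profile does: it falls on a different day with partly different times.

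**3. How many participants**

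The plan gives no sample size for PK, so the Phase II number comes from the Simon design in 10.2 (stop at 5 or fewer responses in 21, otherwise go to 43). Its stated early-termination probability reproduces: P(X ≤ 5 | n = 21, p = 0.25) = 0.567, against 56.7% in the plan. At p = 0.45 it is 0.039.

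Assume that the RP2D is a 10 mg level. Phase I then has 3 + 6 = 9 to 6 + 6 = 12 participants at 10 mg, because the RP2D level needs at least 6. Section 10.2 allows 0 to 6 of them to count in Phase II as well.

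- First-dose 10 mg, stage 2 completes: 9 + 43 - 6 = 46 to 12 + 43 - 0 = 55.
- First-dose 10 mg, Phase II stops at 21: 9 + 21 - 6 = 24 to 12 + 21 - 0 = 33.
- RP2D level alone (Css and second profile): 6 + 43 - 6 = 43 to 6 + 43 = 49, or 6 + 21 - 6 = 21 to 6 + 21 = 27.

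**4. Precision**

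Input: geometric CV of AUC 24-44% (1.2.3.3).

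- Log-scale SD = √ln(1 + CV²) = 0.237 at 24% and 0.421 at 44%.
- The 95% limits are the estimate divided and multiplied by exp(t(0.975, n-1) × SD / √n).
- Example, n = 6 and CV 44%: exp(2.571 × 0.421 / 2.449) = 1.56.

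| n | CV 24% | CV 44% |
|---|---|---|
| 3 | 1.80 | 2.84 |
| 6 | 1.28 | 1.56 |
| 12 | 1.16 | 1.31 |
| 27 | 1.10 | 1.18 |
| 49 | 1.07 | 1.13 |

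At CV 44%, the interval for the geometric mean AUC runs from 64% to 156% of the estimate with 6 participants, and from 89% to 113% with 49.

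**The case against.** Several points on the other side stand.

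- **Omission is not exclusion.** The 10.1 objective cell still names Phase II PK, and the exploratory exposure-response objective could use the data. A reader might infer that the Phase II samples are drawn for no analysis at all; the documents do not support that. What is missing is the secondary endpoint and its summary.
- **The phases may not be replicates.** Section 14.1.7 says an effect of acid-reducing agents on eltanexor PK cannot be ruled out and restricts them during the dose-finding part only. No such limit is stated for Phase II. (Section 3.3.2.2.1 calls for a proton pump inhibitor in thrombocytopenia without a phase limit; the two sections must be reconciled.) Pooling across phases without first showing each would be unsafe.
- **A contrast of 3-6 against about 50 is too strong.** At least 6 participants are required at the RP2D, so the n = 3 factor applies only to other levels. A number near 50 needs stage 2 to complete and a 10 mg RP2D.
- **Cmax is not planned.** It appears only in the background. The planned parameters are AUC, half-life and Css, and for Css a summary by level is appropriate because schedules differ.
- **No decision rule depends on it.** The PK analysis is descriptive with no precision target, and the RP2D rule rests on DLTs. A summary by level does not forbid an additional one by mg dose.

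These points limit the size of the finding and shape the remedy. They do not supply the missing endpoint, and they give no reason to split the C1D8 data by schedule within a phase.

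**Conclusion.** The concern holds. Phase II PK is a stated secondary objective with compulsory sampling, but 10.1 gives it no endpoint and 10.4.3 no analysis. Separately, the level-by-level Phase I summary splits identical first-dose conditions.

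For first-dose AUC at 10 mg, the 95% confidence factor is 1.28-1.56 at the RP2D level with its minimum of 6 participants. Pooled over levels and phases it would be about 1.07-1.13 with 46-55 participants. If Phase II stops at 21, the pooled group is 24-33, where the factor is roughly 1.1-1.2. This rests on the Study 801 variability applying here, a 10 mg RP2D, and no material PK difference between phases. If the RP2D is a 5 mg level, the same argument applies to levels -1 and -2, and Phase II adds nothing at 10 mg.

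The primary endpoints and the dose decision are unaffected. The change should be made because a stated objective would otherwise have no prespecified result.

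**What to change.** In 10.1 and 10.4.3:

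1. Add AUC, half-life and Css as Phase II PK endpoints, summarised descriptively.
2. Summarise C1D8 AUC and half-life by mg dose, pooled over schedule levels. Show Phase I and Phase II separately, then combined, counting any participant who belongs to both once, and report acid-reducing agent use next to these summaries.
3. Keep Css and the second cycle-1 profile by dose level, combining the two phases only at the RP2D level.
4. Reconcile the PK endpoint in 10.1 with 5.1. The endpoint names days 8 and 21, but levels 1 and -2 are sampled on Days 8 and 12.

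The cost is a few lines of text and a little more analysis. No new samples, visits or participants are needed.

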#### **1.1.3 Exploratory Objectives**

- To evaluate the relationship between KPT-8602 exposure (PK) and response
- To evaluate changes in XPO1 mRNA expression and other potential PD markers with treatment
- To assess changes in DNA damage repair by evaluation of gammaH2AX levels
- To evaluate compliance and feasibility of administering PRO in this patient population
- To evaluate tolerability of treatment by assess symptomatic adverse events, physical function and side effect bother
- To longitudinally describe and evaluate disease and treatment-related severity and functional well-being

- To determine meaningful change in disease and treatment-related symptoms and functional well-being by using anchors
- To evaluate changes in DNA methylation status pre- and post-treatment
- To evaluate changes in cell composition in the bone marrow and peripheral blood microenvironment pre- and post-treatment
- To evaluate changes in genetic clonal diversity during treatment
- To evaluate changes in gene expression patterns of tumor suppressor genes and oncogenes (including DNMT3B expression)
- To evaluate the influence of splicing factor mutations (U2AF1, SRSF2, SF3B1, ZRSR2) on nuclear shuttling
- To evaluate the degree of disruption of ribosome biogenesis after XPO1 inhibition
- To evaluate changes in nuclear and cytoplasmic protein composition using mass spectrometry
- To evaluate additional clinical outcomes, such as overall improvement rate (OIR), transfusion-independence (TI), cytogenetic response rate, time to best response (CR, PR, marrow CR + HI, HI), disease-free survival (DFS; definition: time to relapse for participants who achieve CR), progression-free survival (PFS; definition: time to progression or death from MDS), leukemia-free survival (LFS; definition: time to progression to AML or death from any cause), and overall survival (OS; definition: time to death from any cause)

## 1.2 BACKGROUND AND RATIONALE

### 1.2.1 Myelodysplastic syndromes

The myelodysplastic syndromes (MDS) are a group of heterogenous clonal neoplasms of hematopoietic stem cells, characterized by dysplastic changes in at least one myeloid lineage, recurrent genetic aberrations, presence of up to 20% myeloblasts in the bone marrow, and high risk of evolution to acute myelogenous leukemia (AML). Myelodysplasia results in ineffective hematopoiesis with consequential peripheral blood cytopenia(s). Anemia is the most common clinical presentation of MDS, but other cytopenias are also often present. Cytopenias, together with ineffective maturation of neutrophils and platelets, often result in severe and/or recurrent infections and/or bleeding episodes, respectively. In general, it is estimated that up to 1/3 of patients with MDS will die from cytopenia-related complications, up to 1/3 have disease progression into a secondary AML with poor prognosis, and the remaining 1/3 may die from causes unrelated to their MDS.

MDS is a disease of the elderly, with a median age at diagnosis of approximately 75 years, with ~80% of patients being  $\geq 65$  years. Based on cancer registry data, about 10,000 new MDS cases are diagnosed per year in the United States, but the number is probably underestimated, and may be as high as >40,000 based on Medicare claims analyses. There is a slight predominance of males.

Most MDS patients (~90%) have sporadic disease and the remainder are therapy-related MDS (t-MDS), the latter often presenting in patients younger than 60 years of age. In the last decade,

familial related myeloid neoplasia in persons with germ-line mutations (i.e., *RUNX1*, *GATA2*, *DDX41*, *CEPBA*, *ANKRD26*, *ETV6*) is recognized as a predisposing condition for earlier acquisition of additional MDS-related mutations and MDS development.[\(9\)](#) Additionally, MDS can also develop from the rare inherited bone marrow failure disorders, such as Fanconi and Diamond-Blackfan anemia, which can present in childhood and adolescence.[\(10\)](#)

A conceptual model of MDS evolution[\(11\)](#) presumes an initiating somatic driver mutation in the hematopoietic stem cell with subsequent formation of the mutant stem cell clone. The most commonly affected genes involve RNA splicing, DNA methylation, histone modification, transcription regulators, DNA-repair control, signaling and cohesin complex. Six genes are commonly affected and have been reported to be mutant in at least 10% of patients: *SF3B1*, *TET2*, *SRSF2*, *DNMT3A*, *ASXL1*, and *RUNX1*.[\(12\)](#) In the second phase, the mutant clone expands and when it reaches approximately 4% of the total hematopoiesis, clonal hematopoiesis of indeterminate potential (CHIP) can be diagnosed. The duration of the first phase and potential of further progression to the third phase (MDS or clonal cytopenia of undetermined significance [CCUS] – cytopenia with presence of a clonal population without morphologic evidence of dysplastic changes) seems to be related to the genes affected by mutations and the size of the clonal population.[\(13\)](#) Most patients with CHIP and mutations in *DNMT3A*, *TET2*, or *ASXL1* will slowly progress to the third phase, while those harboring spliceosome gene mutations (i.e., *SF3B1*, *SRSF2*, *U2AF1*) will usually progress faster into MDS.[\(13\)](#) The spliceosome gene mutations are collectively present in more than 50% of the subjects with MDS and are mutually exclusive.[\(14, 15\)](#) They are most commonly present in MDS subjects when compared to the patients with other malignancies. In the third phase, clonal predominance of the mutant clone is established with further acquisitions of additional mutations (median of 3).[\(16, 17\)](#) The fourth phase is initiated with the selection of a clone that usually harbors AML-driving mutations (i.e., *FLT3*, *PTPN11*, *WT1*, *IDH1*, *NPM1*, *IDH2* and *NRAS*) leading to progression into secondary AML (s-AML) with  $\geq 20\%$  blasts in the bone marrow.

According to the World Health Organization (WHO) 2016 classification of myeloid neoplasms and acute leukemia,[\(1\)](#) several different MDS-related entities can be discriminated with defined diagnostic criteria such as the number of lineages affected by dysplastic changes, the percentage of blasts in bone marrow, the existence of ring sideroblasts and genetic changes. MDS precursor conditions, such as CHIP and CCUS, are defined by expert panels through a consensus process.[\(18-21\)](#)

The prognosis of MDS depends on disease- and patient-related characteristics. The disease-specific factors with major influence on the prognosis of participants with MDS are the number and depth of cytopenias, the percentage of bone marrow blasts and the cytogenetic aberrations. These factors are incorporated in Revised International Prognostic Scoring System (IPSS-R), currently the most commonly used prognostic index that stratifies MDS patients into 5 prognostic groups predicting overall survival (OS) and time-to-progression to AML.[\(22\)](#) For the purposes of clinical practice, an IPSS-R score of 3.5 is generally accepted as a cutoff for stratifying patients into “higher-risk” MDS (HR-MDS) versus “lower-risk” MDS (LR-MDS) with corresponding median OS of 1.5 versus 5.9 years, respectively.[\(23\)](#) Using this stratification system, about 1/3 of patients with MDS are classified as having HR-MDS and about 2/3 are classified as having LR-MDS.

